#### 9.1.2 Analysis of Secondary Endpoints

The analysis of the first secondary endpoint will be a comparison to the proportions of movements detected by the device and the pregnant women that are true-positives, i.e., those that are also identified by the scan operator, at each of weeks 32, 34, 36, and 38 of pregnancy separately. A z-test of independent proportions will be conducted to detect a difference in the positive predictive value rates for the device compared with the mother, if such a difference exists.

The same analysis will be repeated for the week 32, 34, 36 and 38 visit movements separately. Again, the movements at a particular visit (either week 32, 34, 36 or 38) will be collated across the pregnant women for analysis, and the repeated foetal movements for a given pregnant woman during a particular scan will be treated as independent.

For the second secondary analysis, frequency tables/summary statistics of the responses to the self-reported acceptability questions will be provided please see Appendix 3. The

Formatted: Not Highlight

Formatted: Superscript, Not Highlight

Version 2 April 12th 2021

proportion of women agreeing that the device was acceptable to wear will also be reported, with corresponding 95% confidence interval.

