## 6.2 Primary and Secondary Endpoints/Outcome Measures

#### 6.2.1 Primary Endpoints/Outcome Measures

The primary endpoint of the study is the proportion of movements, as identified by the scan operator, that are successfully detected by the wearable device and the pregnant women, at weeks 32, 34, 36, and 38 of pregnancy. These are the sensitivity rates of the device and pregnant women in detecting foetal movements, treating the scan operator detected movements as the "true" movements.

Fetal movement information noted on the scan would be collected by the operator pressing a foot pedal each time a movement is noted. If the movement persists, another event would be recorded. Fetal movements will be defined as any movement noted by the scan operator. Therefore, a combination of both trunk movements and limb movements will be recorded by the scan operator.

Maternal fetal movements noted would be collected by the mum pressing a button when she felt the movement.

The device will collect movements when the piezoelectric fabric is distorted by fetal movements. Maternal movements such as breathing and vessel pulsation will be filtrated out by software.

All three movements, device, maternally perceived and scan operator recorded will be recorded over 20 mins. The data will be time-stamped to allow matching of the movements, allowing for a degree of error (±500ms) to account for the reaction time of the mother and sonographer.

Raw voltage data collected by the device will be processed and converted to binary movements using an independent "training" subset of the data.

CONFIDENTIAL

Page 9 of 29

Version 2 April 12th 2021

Four separate scans will be undertaken 2 weeks apart. We would aim for these to be in 32nd, 34th, 36th, 38th week. With a margin of flexibility of one week.

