# 6.2.2 Secondary Endpoints/Outcome Measures

The first secondary endpoint of the study is the proportion of movements detected by the device and by the pregnant women that are true-positives, that is those that are also identified by the scan operator, at weeks 32, 34, 36, and 38 of pregnancy. These are the positive predictive values of the device and the pregnant women, which will help understand the extent of false-positive movements and their impact on the usefulness of the wearable device.

The second secondary endpoint of the study is the acceptability of wearing the device as self-reported by the women in a bespoke end of study questionnaire. Please see Appendix 3.

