#### 9 STATISTICS

#### 9.1 Description of Statistical Methods/ Sample size

#### 9.1.1 Analysis of Primary Endpoint

This is a pilot study to test KYMIRA's device on human subjects for the first time, with the primary outcome of interest being its effectiveness in detecting fetal movements, as identified by the operator scanning, compared with those detected by the pregnant women.

The analysis of the primary endpoint will therefore be a comparison of the proportion of movements, as identified by the scan operator, that are successfully detected by the wearable device compared with the proportion detected by the pregnant women, at each of weeks 32, 34, 36, and 38 of pregnancy separately.

The data to be analysed are the binary (Yes/No) outcomes for the device and the mother indicating whether each of the scan operator movements was successfully identified. There will be an outcome for the device and the mother (Yes/No, i.e., Detected/Not detected) for the same scan operator-identified movement. The data are therefore paired and a McNemar's test of paired proportions will be conducted to detect a difference in the proportions of movements detected by the device compared with the mother, if such a difference exists.

The same analysis will be repeated for the week 32, 34, 36 and 38 visit movements separately. The movements at a particular visit (either week 32, 34, 36 or 38) will be collated across the pregnant women for analysis. The repeated foetal movements for a given pregnant woman during a particular scan will be treated as independent.

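### The PPV comparison uses an independent-samples z-test on detections from the same women and scans, so its standard error is not valid, and the direction of the error is unknown

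*Protocol*

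**What the plan says.** Protocol section 6.2.2 defines the first secondary endpoint, PPV, as the share of each source's own detections that the operator also recorded, taken visit by visit. Section 9.1.2 then fixes the test for device against mother: "A z-test of independent proportions will be conducted to detect a difference in the positive predictive value rates". It collates the data across women at each visit and makes a further assumption about clustering, namely that "the repeated foetal movements for a given pregnant woman during a particular scan will be treated as independent".

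The design sections describe how these data arise. Section 6.2.1 states that "All three movements, device, maternally perceived and scan operator recorded will be recorded over 20 mins", and it has events from the three sources matched by time stamp within ±500 ms. Section 7.1 has the woman wearing the fabric and holding the button during the same scan.

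For sensitivity, section 9.1.1 notes that both sources yield a result on each operator movement, and concludes: "The data are therefore paired and a McNemar's test of paired proportions will be conducted".

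**The concern.** The device PPV and the maternal PPV are not estimates from two separate samples. Every woman with detections from both sources feeds both proportions, and one operator event can be a true positive for both. A z-test of independent proportions takes the variance of the difference as the sum of two binomial variances. The correct variance is V(device) + V(mother) − 2·Cov, with each V allowing for clustering within woman. Two terms are therefore missing, and they act in opposite directions.

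This matters because sensitivity does not penalise false detections. Of the listed endpoints, PPV is the one that does, and section 6.2.2 gives that as its purpose. If the PPV difference is reported with a p-value from this test, a reader cannot tell whether that p-value is too small or too large.

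**Working it through.** **The plan's own figures.** No sample size or power is stated for PPV. The primary calculation reproduces. With sensitivities 0.60 and 0.44 and the minimum phi, the discordant probabilities are 0.56 and 0.40, so n = (1.960 + 1.282)² × 0.96 / 0.16² = 394.03, rounded up to 395. Then 395/10 = 39.5, giving 40 women; adding 3 for training gives 43; 43/0.8 = 53.75, giving 54. None of this uses the PPV test.

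**Assumptions** (the protocol gives no PPV, ICC or overlap). 40 women; detections per woman varying as Poisson with mean 10 (device) and 7 (mother), so 400 and 280 in total; true PPV 0.6 for both.

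**Variance used by the z-test.** 0.6 × 0.4 × (1/400 + 1/280) = 0.001457; SE 0.0382.

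**Clustering only.** Let ρ be the correlation between a woman's device effect and her maternal effect.

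Variance = (0.24/400)(1 + 10·ICC) + (0.24/280)(1 + 7·ICC) − 2·ρ·ICC·0.24/40

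True size = 2Φ(−1.96 × z-test SE / true SE)

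Example, ICC 0.10:
- ρ = 0: 0.001200 + 0.001457 = 0.002657; SE ratio 0.741; size 14.7%.
- ρ = 0.5: subtract 0.0006, leaving 0.002057; ratio 0.842; size 9.9%.
- ρ = 1: subtract 0.0012, leaving 0.001457; ratio 1.00; size 5.0%.

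| ICC | ρ = 0 | ρ = 0.5 | ρ = 1 |
|---|---|---|---|
| 0.02 | 6.9% | 6.0% | 5.0% |
| 0.05 | 9.9% | 7.4% | 5.0% |
| 0.10 | 14.7% | 9.9% | 5.0% |
| 0.20 | 22.8% | 14.7% | 5.0% |

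Beta-binomial simulation agrees with these to within about one percentage point. A woman-level robust test held 5 to 7% in the same clustered scenarios.

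**Shared detections only, no clustering.** If a fraction f of maternal detections coincide with a device detection and share its true or false status, Cov = f × 0.24/400.
- f = 0.25: 0.001457 − 0.000300 = 0.001157; ratio 1.12; size 2.8%.
- f = 0.50: 0.001457 − 0.000600 = 0.000857; ratio 1.30; size 1.1%.
- f = 0.90: 0.001457 − 0.001080 = 0.000377; ratio 1.97; size about 0.0%.

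**Same check with the protocol's sensitivities and an assumed PPV of 0.70.** Detections: 400 × 0.60/0.70 = 343 and 400 × 0.44/0.70 = 251. The z-test SE is 0.0381. With 25%, 50% and 75% overlap the correct SE is 0.0338, 0.0289 and 0.0230, and the size is about 2.7%, 1.0% and 0.1%.

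**Power at 90% overlap.** Take 252 shared detections and 28 maternal-only detections, all with PPV 0.6, and 148 device-only detections with a lower PPV. If the device-only PPV is 0.3, the device PPV is (252 × 0.6 + 148 × 0.3)/400 = 0.489, a deficit of 0.111.
- True variance: 252 × 0.24 × (1/280 − 1/400)² + 148 × 0.21/400² + 28 × 0.24/280² = 0.000349; SE 0.0187.
- The pooled PPV is 0.535, so the z-test SE is 0.0389 and it rejects beyond 0.0762.
- Rejection probability: Φ((0.111 − 0.0762)/0.0187) = about 97%.

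The same steps for device-only PPV 0.4 and 0.5 give:

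| Device PPV | z-test rejects | With the correct SE |
|---|---|---|
| 0.563 | about 3% | about 47% |
| 0.526 | about 46% | about 97% |
| 0.489 | about 97% | about 100% |

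**The case against.** **The change of test was needed.** Each PPV has its own denominator, and a false detection by one source need not have a counterpart from the other, so McNemar's test cannot simply be carried over from sensitivity. This stands. A reader might infer that the protocol should have reused McNemar's test, and that would be wrong. But different denominators do not make two samples independent.

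**A reader might infer that the test has almost no power.** The near-zero rejection rate at 90% overlap is computed under equal PPVs, so it is the size of the test, not its power. Power is lost for small gaps, but a deficit of about 11 points is still found about 97% of the time.

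**A reader might infer that false-positive findings are bound to be inflated.** The documents do not support this either. The inflated sizes come only from within-woman clustering; the missing device–mother covariance, if positive, acts the other way. With perfectly correlated woman effects the two cancel. At ICC 0.02 the excess is one to two percentage points, and no ICC is given that would favour 0.10 or 0.20.

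**The endpoint is secondary in a study that section 9.1.1 calls a pilot.** No decision rule or sample size rests on this p-value, and the PPV estimates serve the descriptive purpose in section 6.2.2 whichever test is used. This stands and sets the priority. It does not make the standard error valid.

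**Conclusion.** The point holds in a limited form. Section 9.1.2 fixes a test whose independence assumptions, between device and mother and between movements within a woman, are contradicted by the simultaneous recording and shared operator reference in sections 6.2.1, 6.2.2 and 7.1.

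Under the stated assumptions, the true size of the nominal 5% test runs from about 0% (heavy overlap, no clustering) to about 23% (ICC 0.20, unrelated woman effects), with values near 5% possible in between. The documents fix neither the size nor the direction of the error, so the p-value cannot be corrected by judgement afterwards. What is affected is the standard error, confidence interval and p-value for the PPV difference at all four visits. The collated PPVs, their difference, and the 395-movement and 54-woman figures are not affected. This should be fixed before analysis, but as a secondary-endpoint matter it is not critical to the study.

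**What to change.** In section 9.1.2, or in the SAP, replace the z-test at each visit with one of the following:
- Stack device and maternal detections and fit a marginal (GEE) model of true-positive status on source (device or mother), with independence working correlation and robust variance clustered on woman.
- Bootstrap whole women and recompute the PPV difference in each resample.

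Report the PPV difference with its 95% confidence interval, and delete the statement in section 9.1.2 that movements within a woman are treated as independent. Either method covers both the device–mother covariance and the clustering.

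The cost is a change of wording and a few lines of code. Time-stamped events and participant numbers are already collected, so no further data, visits or participants are needed.

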#### 9.1.3 Other Analyses

In addition to the analysis of the primary endpoint outlined above, an additional exploratory analysis may be conducted, pooling the data across visits and comparing the overall proportions of movements detected by the device compared with the mothers.

Summary statistics will be provided for subject demographics, medical history, and baseline measures.

#### 9.7 Inclusion in Analysis

All data collected from scanning whilst wearing the data will be analysed. Even if the patient leaves the study prior to completing all 4 scans.

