## 9.1.1.1 Sample Size Determination

Previous studies that compared the number of fetal movements observed by ultrasound and those perceived by mothers during the 3rd trimester (Brown R, 2016) (Hertogs K, 1979) found the later to be highly varied; with different studies reporting different average fractions in the range of 0.16 to 0.44 (Hertogs K, 1979). Hence, we calculated the sample size for an

CONFIDENTIAL

Formatted: Not Highlight

Formatted: Superscript, Not Highlight

Formatted: Not Highlight

Page 17 of 29

Version 2 April 12th 2021

assumed sensitivity rate of 44% for the pregnant mothers, corresponding with the most conservative estimate, i.e., to ensure adequate power. Based on the initial simulation tests of our device, we expect it to detect 0.8 to 0.9 fraction of the fetal movements. Allowing for a potentially lower detection rate in clinical practice, we assumed a sensitivity rate of 60% for the wearable device, again corresponding a larger sample size to ensure sufficient power.

For a single visit (week 32, 34, 36 or 38), based on a two-sided McNemar's test with a 5% significance level and 90% power, 395 movements are required (according to Lachenbruch (1992) (Lachenbruch, 1992) and based on the minimum estimate of the phi correlation r). Each pregnant woman is expected to have a minimum of around 10 foetal movements per 20 minute scan, as detected by the sonographer, therefore (rounding up) approximately 40 subjects are required for the study analysis.

In addition, an independent "training" subset of the data are required for calibrating the device. It is estimated that 3 subjects will be required for this purpose (i.e., approximately 30 movements), taking the number of subjects in the study to 43. Allowing for a drop-out rate of approximately 20%, a final sample size of 54 subjects (again rounding up) are estimated to be required for recruitment into the study. As the sample size required is based upon the number of foetal movements, if a different number of movements per mother is observed than assumed, the number of subjects recruited will be amended to ensure an appropriate total number of movements available for analysis.

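### Section 9.7 analyses all scan data with no exception, which conflicts with the separate training subset in 6.2.1 and 9.1.1.1 and, read literally, scores the device partly on its own calibration data

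*Protocol*

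**What the plan says.** - **Protocol 6.2.1 (primary endpoint):** "Raw voltage data collected by the device will be processed and converted to binary movements", and this is done with a training subset that the section calls independent.
- **Protocol 9.1.1.1 (sample size):** about 40 women are needed for the analysis. A training subset, again called independent, is then added so that the device can be calibrated. On its size the section says: "It is estimated that 3 subjects will be required for this purpose". They are expected to supply about 30 movements and bring the total to 43 women. Drop-out of about 20% brings recruitment to 54.
- **Protocol 9.1.1 (primary analysis):** the movements at a visit "will be collated across the pregnant women for analysis". Section 9.1.2 does the same for positive predictive value. Neither section excludes anyone.
- **Protocol 9.7 (inclusion in analysis):** "All data collected from scanning whilst wearing the data will be analysed". The next sentence is a fragment: "Even if the patient leaves the study prior to completing all 4 scans".

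No section says that the training women are left out of the sensitivity or predictive-value analyses.

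**The concern.** The training women wear the device while being scanned, so their data fall under 9.7 as worded. The same data cannot be independent of the evaluation and also part of it.

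The primary analysis is a paired comparison of device and mother on the same operator-identified movements. Only the device side is calibrated on study data; the mothers' button presses are not. A classifier usually does better on the data that set it up than on new data. Any such gain would enter the device-minus-mother difference on one side only, in the device's favour. It could carry over to the device's positive predictive value.

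**Working it through.** **1. Reproduce the plan's own number.** Inputs from 9.1.1.1: mother 0.44, device 0.60, two-sided 5%, power 90%, minimum phi, 10 movements per woman per scan, 3 training women, 20% drop-out.

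At the minimum feasible phi, the probability that both detect a movement is 0.44 + 0.60 − 1 = 0.04. The discordant cells are 0.60 − 0.04 = 0.56 and 0.44 − 0.04 = 0.40, so total discordance D = 0.96. The difference d = 0.16.

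- n = (1.960 + 1.282)² × D / d² = 394.03, rounded up to 395.
- Variants: 390 with the variance under the alternative, and 397 with a continuity correction. The stated 395 is reproduced.
- 395 / 10 = 39.5, giving 40 women. 40 + 3 = 43. 43 / 0.80 = 53.75, giving 54.

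The chain reproduces with the 3 training women outside the 40 who are analysed.

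**2. What 9.7 gives if followed literally.** It gives 43 women and about 430 movements per visit, instead of 40 women and about 400. The training women's share is 3 / 43 = 7.0%.

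**3. Effect on device sensitivity.** Let s be the true device sensitivity and t the sensitivity on the training women's movements. Pooled sensitivity is (40s + 3t) / 43, so the shift is (3/43) × (t − s). The protocol does not give t, so a range is assumed.

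| True s | Assumed t | Shift (percentage points) |
|---|---|---|
| 0.60 | 0.70 | 0.7 |
| 0.60 | 0.80 | 1.4 |
| 0.60 | 0.90 | 2.1 |
| 0.60 | 1.00 | 2.8 |
| 0.80 | 1.00 | 1.4 |
| 0.90 | 1.00 | 0.7 |

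The last two rows use the 0.8 to 0.9 that 9.1.1.1 expects from simulation tests, with a perfect training fit. Against the planned 16-point difference, the range for s = 0.60 is 0.7/16 = 4% to 2.8/16 = 17%.

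**4. Effect on the test if the device is no better than the mothers.** Set both true sensitivities to 0.44 and t to 0.60 to 1.00. The shift is (3/43) × 0.16 = 1.1 points up to (3/43) × 0.56 = 3.9 points. Dividing by √(D/430) gives the shift in the test statistic.

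- Minimum phi, D = 0.88: the nominal 5% test rejects about 5.7% to 14% of the time.
- Device and mother detecting independently, D = 2 × 0.44 × 0.56 = 0.493: about 6.3% to 21%.

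These are normal approximations and use the protocol's own assumption that movements are independent.

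**5. After the fix.** With the 3 women excluded, 40 women and about 400 movements remain. Power is about 0.907 (0.904 at 395), so the planned 90% is kept with 54 recruited.

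**The case against.** The strongest reply is that 9.7 answers a different question. Its second sentence is about women who leave early and agrees with 6.6, which keeps the scans of women who deliver before the last visit. The two sections that do discuss training call the subset independent, and 9.1.1.1 counts it separately. A specific statement would normally govern a general one, and the collation wording in 9.1.1 describes pooling within a visit rather than an analysis set. As an account of intent this is probably right. It does not remove the conflict: the only inclusion rule says all, nothing excludes the training women, and an analyst who followed 9.7 would include them.

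Other parts of the reply stand and limit the point:

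- **Size.** The 2.8 points need perfect detection on the training data, which is doubtful when events are matched within ±500 ms to allow for human reaction time. It is a ceiling.
- **Share.** About 30 training movements equals 3 women × 10 movements × one scan. If that is the whole training set, training events are 7% of one visit but 30 / (43 × 10 × 4) = 30/1,720 = 1.7% over four visits. The protocol does not say whether the 30 is per visit, or what becomes of these women's other scans.
- **Reference for calibration.** A reader might infer that the algorithm is fitted to the operator's pedal presses. That is plausible, but the protocol says only that the subset is used for conversion and calibration.
- **Choice of training women.** A reader might also infer that they could be picked after the data are seen. The protocol does not say so. Which women they are, and when the algorithm is locked, is detail that a statistical analysis plan may supply, so it is not counted here.

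**Conclusion.** The point holds as a contradiction in the text. Section 9.7, taken as written, conflicts with the independent training subset in 6.2.1 and with the 40 + 3 count in 9.1.1.1. Any resulting bias favours the device.

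For a true device sensitivity of 0.60 and an assumed training-set sensitivity of 0.70 to 1.00, the bias is about 0.7 to 2.8 percentage points at a visit. It is less if the true sensitivity is 0.8 to 0.9, or if only one scan per training woman was used for calibration. These figures take 43 women with equal numbers of movements. No figure can be put on the predictive value, because the protocol gives no assumption for it.

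A reader might go further and conclude that the sponsor has decided to evaluate the device on its calibration data, or that the primary result would be driven by it. The documents do not support either. The inclusion looks unintended, and on the planning figures even the ceiling is about a sixth of the planned difference. The inflated rejection rates in the working matter only if the device is in truth no better than the mothers.

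**What to change.** Reword 9.7 along these lines:

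*All scan data from women outside the training subset will be analysed, including data from women who leave before completing all four scans. All scans of the women in the training subset are excluded from the sensitivity analysis (9.1.1), the positive-predictive-value analysis (9.1.2) and the pooled exploratory analysis (9.1.3). Their acceptability and safety data are retained.*

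Excluding all scans of these women, and not only those used for calibration, also settles what happens to their remaining visits. The same edit can correct the slip in 9.7's first sentence.

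The cost is a few sentences, best made before any device data are processed. No extra participants are needed: recruitment stays at 54, which already includes the 3 training women, and power stays at about 90% under the plan's assumptions.
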